### **Overall Survival**

Proportion of patients alive (survival rate) after 24, 48 and 72 weeks for full group and subgroup as available will be presented by treatment groups and overall. Kaplan-Meier plots will be presented, and treatment groups will be compared using a log-rank test.

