#### 6.5. Early Discontinuation/Withdrawal of Participants

Subjects may withdraw consent at any time for any reason or be dropped from the trial at the discretion of the investigator should any untoward effect occur. In addition, a subject may be withdrawn by the investigator or the Sponsor if enrolment into the trial is inappropriate, the trial plan is violated, or for administrative and/or safety reasons.

In this trial, a subject may discontinue from treatment but continue to participate in the regularly scheduled activities, as long as the subject does not withdraw consent. Once a subject has discontinued treatment, he/she may be allowed to start treatment again after consultation with the investigator, if discontinuation of treatment is  $\leq$  2 weeks.

A subject must be discontinued from the trial for any of the following reasons:

- The subject withdraws consent.
- The subject has a medical condition or personal circumstances which, in the opinion of the investigator and/or Sponsor, places the subject at unnecessary risk if participation in the trial is continued.
- The subject reaches the criteria for respiratory insufficiency (tracheostomy or the use of non-invasive ventilation for >20 hours per day for >10 consecutive days),

A subject must be discontinued from study treatment (but should continue to be monitored in the study) for any of the following reasons:

1-The subject becomes pregnant during the study.

2-The subject's investigator considers it is in the best interest of the subject to discontinue including worsening or disease progression if the investigator considers that it is in the patient's best interest the initiation of any standard of care treatment prohibited in the study

3-Serious adverse event considered related to the IMP

4-Severe Neurotoxicity considered related to the IMP

5-Any other severe adverse event considered related to the IMP at the discretion of the investigator.

6-Acute renal failure (creatinine clearance of less than 30 mL/min as calculated by the Cockcroft Gault equation)

7-Severe liver disorder defined as:

- ALT/AST  $\geq$  3xULN and bilirubin  $\geq$  2xULN ( $>35\%$  direct bilirubin)
- ALT/AST  $\geq$  8xULN
- ALT/AST  $\geq$  3xULN and with symptoms believed to be related to liver injury or hypersensitivity.
- ALT/AST  $\geq$  3x baseline ALT/AST and with symptoms believed to be related to liver injury or hypersensitivity.

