#### 8.1.2. Survival Time

If a patient dies during the 72 weeks of participation, the date of death will be recorded in the eCRF. If a patient reaches the criteria for respiratory insufficiency (tracheostomy or the use of non-invasive ventilation for >20 hours per day for >10 consecutive days), the date this criterion was met will be recorded in the eCRF and the patient will no longer be part of the study.

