### 11.4. Study Estimand and Handling of Missing Data

To be noted that in this study all efforts will be made to ensure collection of data up to week 48 for all randomized subjects and at least for 100 subjects up to week 72 regardless of treatment withdrawal or protocol deviations.

As per the ICH E9(R1) (*draft addendum on estimands and sensitivity analysis in clinical trials*), the plan for the assessment of the Primary endpoint (PEP) is described here after using the 4 attributes of the estimand:

1. Population: ALS patients fulfilling the selection criteria, as described in section 5 of this protocol
2. Primary endpoint (PEP): Change from baseline in Amyotrophic Lateral Sclerosis Functional Rating Scale – Revised (ALSFRS-R) score after 48 weeks (see sections 3.2.1 and 11.3.4.1)
3. Intercurrent events (IE): The assumptions and expectations on the relevant intercurrent for this study have been based on the publication of a similar trial (Cudkowicz et al., 2013)
4. Accordingly, the following situations have been identified:
  - a. No treatment initiation with the IMP: exclusion from the main analysis with the mFAS population.
  - b. Treatment discontinuation because of adverse events: expected rates  $\approx 3$  (control arm) - 7% (experimental arm).
  - c. Treatment discontinuation because of lack of efficacy: expected rates  $\approx 5$  (control arm) 10% (experimental arm).
  - d. Other treatment related reasons (i.e. due to efficacy or safety issues). To this category will apply other treatment related reasons that those specified in "b" and "c", even that, *a priori*, no potential scenarios are foreseen at the moment of the planning.
  - e. Rescue medication. No clear prevalence rates can be ascertained, but differential higher rates are expected in placebo. This situation is likely to be closely related to IE #c.
  - f. Non treatment-related reasons, others than specified in this list of IE: very low expected rates (i.e.  $\le 1\%$ ). This will also situations like patients moving (not because bad prognosis) to another location or death for completely treatment-unrelated reasons.
  - g. Related death (or death with unknown reasons): it is expected that the rate of death at 52 weeks will be lower than the observed in that trial ( $< 17\%$ ). A non-substantial but lower rate is expected in the experimental arm.

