### **‘Survival Time’**

‘Survival Time’, i.e. time to death or time to reaching the criteria for respiratory insufficiency is the other key secondary endpoint. The criteria for respiratory insufficiency are defined as tracheostomy or initiation of non-invasive ventilation for more than 20 hours a day for more than 10 consecutive days, over 48 weeks or 72 weeks, respectively. Descriptive statistics (median and Q1/Q3 quartiles with 95% confidence intervals) and Kaplan-Meier curves will be provided. The difference between oral FAB122 and placebo will be assessed using restricted mean survival time (RMST) analysis for the time point week 48 (and another one for week 72 for the subgroup of 100 patients), adjusting for the stratification variables. The RMST analysis provides robust estimates even when the proportional hazard function is violated.

SAS PROC LIFETEST with option RMST will be used for this analysis.

In addition, a Cox regression model and a stratified log-rank test will also be applied as supportive analysis, including factors for treatment and stratification variables. Patients that complete the study and those that discontinue due to reasons other than death or due to reaching the criteria for respiratory insufficiency will be considered censored.

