### **ALSFRS-R score**

Absolute and change from baseline in total ALSFRS-R score after 24 (full group and subgroup) and 72 weeks (subgroup only) will be presented by treatment group in summary tables. Note that results after 12, 48 and 60 weeks for full group/subgroup as available will also be presented by treatment group in the same summary table. The statistical analysis is as described in the section on the primary endpoint.

The proportion of patients with change from baseline in ALSFRS-R score at 24, 48 and 72 weeks will be presented in categories for each treatment group. Categories will include change  $\geq 0$ , change between  $< 0$  and  $\geq -1$ , change between  $< -1$  and  $\geq -2$  etc. A Chi-squared test will be performed, and the p-value added to the table.

The slope of the decrease in ALSFRS-R total score over time at 24, 48 and 72 weeks will be calculated and presented in summary tables. Per treatment arm, slopes will be determined using an MRMM model on the change from baseline, with independent variables treatment group, baseline value, time and treatment\*time interaction. Slopes for each treatment group and slope difference between treatments will be presented. No individual per-patient slopes will be presented.

---

 Where date of death is taken from the Survival follow-up form.

Change from baseline in ALSFRS-R subscale scores will also be calculated after 24, 48 and 72 weeks for the following subscales:

- Bulbar function (question 1-3 of the ALSFRS-R);
- Fine motor function (question 4-6 of the ALSFRS-R);
- Gross motor function (question 7-9 of the ALSFRS-R)
- Respiratory function (question 10-12 of the ALSFRS-R);

Summary statistics for the change from baseline in the above subscale scores will be presented by treatment group and overall, again separately for the full group and the subgroup.

In addition, a similar statistical model as for the primary endpoint will be utilized for analyzing the change from baseline for the subscale scores.

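### The protocol ends participation at respiratory insufficiency, but overall survival is analysed to week 72 with no stated vital-status follow-up or censoring rule after that exit

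*SAP*

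**What the plan says.** Protocol 6.5 has two separate lists. One covers stopping study treatment while remaining under observation. The other covers leaving the trial altogether: "A subject must be discontinued from the trial for any of the following reasons". RI is in the second list: "The subject reaches the criteria for respiratory insufficiency", meaning tracheostomy or non-invasive ventilation for more than 20 hours a day for more than 10 consecutive days. Protocol 8.1.2 agrees: "the date this criterion was met will be recorded in the eCRF and the patient will no longer be part of the study". The same section ties the recording of a death to the 72 weeks of participation.

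SAP 5.6.2, Overall Survival, takes death alone as the event: "Proportion of patients alive (survival rate) after 24, 48 and 72 weeks for full group and subgroup as available will be presented". It adds: "Kaplan-Meier plots will be presented, and treatment groups will be compared using a log-rank test". It states no censoring rule.

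The nearest censoring sentence belongs to the composite key secondary endpoint, Survival Time, in which RI is itself an event. It opens "Patients that complete the study and those that discontinue due to reasons other than death or due to reaching the criteria for respiratory insufficiency will", and ends by censoring these patients. Footnote 4 to that endpoint reads: "Where date of death is taken from the Survival follow-up form". Neither document gives the form's schedule, its duration or its status after trial exit.

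On the expected number of deaths, Protocol 11.4 says, with reference to a similar published trial, that "it is expected that the rate of death at 52 weeks will be lower than the observed in that trial", and gives the figure as below 17%.

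**The concern.** Overall survival needs to know whether each patient is alive at weeks 24, 48 and 72. A mandatory exit at RI removes that information unless someone goes on collecting it. Without it, an analyst has two options, and both err in the same direction:

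- **Censor at RI.** Kaplan-Meier then assumes that these patients go on to die at the rate of patients still under observation. Protocol 2.1 gives respiratory failure as the cause of death in 66-81% of ALS patients, so that assumption is doubtful.
- **Keep them in the proportion alive.** They are then counted as survivors.

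Either way, survival is overstated within each arm. The log-rank comparison is also affected if the arms differ in how often RI occurs.

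Survival is the first secondary objective, and overall survival is the listed efficacy endpoint with death alone as the event. Two other analyses also use deaths: CAFS (SAP 9.1), the second step of the testing hierarchy, and the mortality part of the joint model (SAP 5.6.3). In CAFS, a patient who left at RI and died unrecorded would be compared on function rather than on death.

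**Working it through.** The documents state no overall-survival rate, RI rate or post-RI mortality, so there is no figure of the plan's to reproduce on this point. The size can only be shown over assumptions.

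**From the documents:** 200 FAB122 and 100 placebo patients; assessment at weeks 48 and 72; deaths expected below 17% at 52 weeks.

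**Assumed:** death without RI by week 48, D = 13%; RI by week 48, R = 3%, 6% or 10%; death after RI, m = 5%, 10% or 20% a month; all hazards constant.

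**Formulas**, with T in months (week 48 = 48 × 7 / 30.44 = 11.04):

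- Total hazard h = −ln(1 − D − R) / 11.04, split as h_d = h·D/(D+R) and h_r = h·R/(D+R).
- Post-RI hazard h_m = −ln(1 − m).
- Dead after RI by T = h_r × [(1 − e^(−hT))/h − (e^(−hT) − e^(−h_m·T))/(h_m − h)].
- True mortality = death without RI + death after RI.
- Kaplan-Meier mortality with RI censored = 1 − e^(−h_d·T).

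**Worked case, R = 6%, m = 10%:** h = −ln(0.81)/11.04 = 0.01909, h_d = 0.01306, h_r = 0.00603, h_m = 0.1054. Dead after RI = 0.00603 × [0.19/0.01909 − (0.81 − 0.3125)/0.0863] = 2.5%. True mortality = 13.0 + 2.5 = 15.5%. Kaplan-Meier mortality = 1 − e^(−0.1442) = 13.4%. The error is 2.1 points, or 2.5 points if these patients are simply counted as alive. One standard error of a single-arm proportion of 15.5% is 2.6 points at n = 200 and 3.6 points at n = 100.

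| RI by wk 48 | Death after RI per month | True deaths wk 48 | KM deaths wk 48 | Error wk 48 (points) | True deaths wk 52 | Error wk 72 (points) |
|---|---|---|---|---|---|---|
| 3% | 5% | 13.7% | 13.2% | 0.5 | 14.8% | 1.0 |
| 3% | 10% | 14.3% | 13.2% | 1.1 | 15.4% | 1.9 |
| 3% | 20% | 14.9% | 13.2% | 1.7 | 16.1% | 2.8 |
| 6% | 5% | 14.5% | 13.4% | 1.0 | 15.7% | 2.0 |
| 6% | 10% | 15.5% | 13.4% | 2.1 | 16.8% | 3.8 |
| 6% | 20% | 16.9% | 13.4% | 3.4 | 18.3% | 5.6 |
| 10% | 5% | 15.5% | 13.7% | 1.7 | 16.8% | 3.3 |
| 10% | 10% | 17.2% | 13.7% | 3.5 | 18.7% | 6.2 |
| 10% | 20% | 19.5% | 13.7% | 5.7 | 21.1% | 9.2 |

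The rows below 17% at week 52 have week-48 errors of 0.5 to 2.1 points. The three rows with errors of 3.4 points or more exceed 17%.

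**Sensitivity to the 13%.** The ceiling alone does not cap the error near 2 points; the 13% does much of that work. With D = 10%, R = 5% and half of RI patients dead within 26 weeks, the error is 2.0 points at week 48 (survival 0.897 against 0.878) and 3.5 at week 72. With D = 6%, R = 10% and 80% dead within 26 weeks, true mortality is only 14.1% at week 52, yet the error is 6.6 points at week 48 and 10.7 at week 72. At R = 1%, with D = 13% and the monthly rates above, the week-48 error is 0.2 to 0.6 points.

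**Between arms.** With the same hazards in both arms, the level errors are equal and cancel in the difference. As an illustration, 3% RI on FAB122 and 6% on placebo at 10% a month give a true mortality difference of 15.52 − 14.26 = 1.26 points. Kaplan-Meier would show 13.43 − 13.21 = 0.22. In this example the bias runs against the drug.

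**The case against.** The strongest reply is that the deaths may well be captured. The SAP takes dates of death from a dedicated form and is written against a blank CRF that is not among the documents. If that form is completed after RI, the error is zero. A reader might infer from Protocol 8.1.2 that every patient is lost at RI and that all later deaths are censored. The documents do not support this: that section says nothing about vital status after exit, and the SAP has no rule making RI a censoring event for overall survival.

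Other follow-up language also helps in part. Protocol 11.3.3 promises efforts to follow all subjects to 48 or 72 weeks. Protocol 9.6.1 allows follow-up of serious adverse events after a patient leaves the study, although 9.1.1 generally keeps planned ventilation set-up out of that category. Protocol 11.4 commits to data collection to week 48 despite treatment withdrawal or protocol deviations, but an exit required by the protocol is neither. None of this text requires vital status after RI.

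On importance, Protocol 2.1 says that the effect on survival is assessed through the key secondary endpoints, and SAP 5.6 treats endpoints outside the hierarchy as strictly explorative. The composite Survival Time counts RI as an event, so this gap does not arise there. Protocol 2.1 also describes non-invasive ventilation as prolonging survival and gives no mortality rate after RI. These points stand, and they lower the priority. They do not remove the conflict between the exit rule and an endpoint that needs vital status after it.

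**Conclusion.** The two documents are not reconciled. The protocol ends participation at RI, the SAP analyses all-cause death to week 72, and nothing says whether deaths between the two are collected or how such patients are censored. If they are not collected, overall survival is overstated in each arm, and the comparison is biased if RI rates differ.

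The size rests on assumed rates. With 13% death without RI by week 48 and total deaths under 17% at week 52, the week-48 error is about 0.5 to 2 points. It is larger at week 72, with higher assumed rates, or where more of the deaths follow RI. It is close to zero if RI is rare, and zero if the form captures these deaths. A reader might want to quote a fixed bias of several points; the documents give no RI rate or post-RI mortality from which to derive one.

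Nor should the point be read as undermining the confirmatory results. Overall survival is exploratory, and Survival Time is unaffected. CAFS and the joint model do depend on death dates and would benefit from the same clarification, but no effect on them has been quantified. Priority is modest.

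**What to change.** - **Protocol 6.5 and 8.1.2:** reconcile with SAP 5.6.2 by stating that vital status (alive, or date of death) is recorded after RI up to the patient's planned week 48 or 72, on the existing Survival follow-up form. If this is already done, say so.
- **SAP 5.6.2, Overall Survival:** state that RI is not a censoring event and that patients are censored at the date last known alive. Use the same death dates for CAFS and the joint model.
- **If vital status after RI cannot be obtained for some patients:** report how many per arm and add a sensitivity analysis over assumed post-RI mortality.

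Treatment and visit rules are unchanged. The cost is a short clarification in each document and a vital-status check per affected patient. At the assumed 3-10% RI by week 48, that is about 9 to 30 of 300 patients.

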### **Progression free survival**

Proportion of patients alive and no tracheostomy, or no initiation of non-invasive ventilation for more than 20 hours a day for more than 10 consecutive days after 24, 48 and 72 weeks will be presented by treatment group. Kaplan-Meier plots will be presented, and treatment groups will be compared using a log-rank test.

### **Staging of disease progression**

Data from staging of disease progression (King's scaling system, MiToS) after 12, 24, 60, 72 weeks as compared to baseline will be presented per visit by treatment group and overall, in summary tables using frequency and percentages. Frequency and percentages of patients showing a decline of  $\geq 1$  stage from baseline will be presented as well.

Kaplan-Meier curves will be created to present time to decline of  $\geq 1$  stage from baseline in both staging systems over 48 weeks or 72 weeks, respectively. A log-rank test will be used to determine the difference between study arms. Patients lost to follow-up will be censored. Days of maintaining the baseline stages will be presented per treatment arm and group/subgroup, including differences between treatment groups.

See section 9.1 for relevant derivations for King's scaling system and MiToS.

### **Slow Vital Capacity (SVC)**

Relevant derivations for the SVC are presented in section 9.1.

Descriptive statistics for absolute value and change from baseline in slow vital capacity (SVC, liters) at 24, 48 and 72 weeks will be presented in by treatment group and overall. A similar statistical model as for the primary endpoint will be utilized for analyzing the change from baseline.

### **Hand-held dynamometer**

Derivations for the HDD megascore are presented in section 9.1.

Descriptive statistics for absolute value and change from baseline in the overall mega score for the hand-held dynamometer (HHD) at 24, 48 and 72 weeks will be presented by treatment group and overall. A similar statistical model as for the primary endpoint will be utilized for analyzing the change from baseline for the overall mega score. Subscores (per muscle and per muscle group) will only be included in the listings.

### **QoL**

The following QoL parameters will be calculated and presented by treatment group and overall in summary tables.

- Absolute values and change from baseline in the total score on the ALS Assessment Questionnaire-40-Item (ALSAQ-40) and the five scale scores at 24, 48 and 72 weeks. Scale scores will also be presented based on range, using frequency and percentages. A similar statistical model as for the primary endpoint will be utilized for analyzing the change from baseline for the total score only. Derivations for the ALSAQ-40 are presented in section 9.1.
- EuroQoL – 5 Dimensions-5 Levels (EQ-5D-5L) questionnaire score 24, 48 and 72 weeks. Frequency and percentage of each level will be presented for each timepoint on each of the dimensions, per treatment. Relevant derivations for the EQ-5D-5L are presented in section 9.1. The per patient 5-digit number will only be presented in the listing.
- Absolute values and change from baseline Health related QoL Visual Analogue Scale (VAS) score at 24, 48 and 72 weeks. Data from all visits collected will be presented in the summary. A similar statistical model as for the primary endpoint will be utilized for analyzing the change from baseline.

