#### QoL

1. Change from baseline in the total score on the ALS Assessment Questionnaire-40-Item (ALSAQ-40) Form at 24, 48 and 72\* weeks;
2. Change from baseline in EuroQoL – 5 Dimensions-5 Levels (EQ-5D-5L) questionnaire score at 24, 48 and 72\* weeks.
3. Change from baseline in Health related QoL Visual Analogue Scale (VAS) score at 24, 48 and 72 weeks.

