### QoL

- Change from baseline in the total score on the ALS Assessment Questionnaire-40-Item (ALSAQ-40) Form at 24, 48 and 72 weeks;
- Change from baseline in EuroQoL – 5 Dimensions-5 Levels (EQ-5D-5L) questionnaire score at 24, 48 and 72 weeks.
- Change from baseline in Health related QoL Visual Analogue Scale (VAS) score at 24, 48 and 72 weeks.

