## Health economics

Cost-Utility analysis of treatment with FAB122.

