### Cost-utility analysis

In this study, an exploratory cost-utility analysis for treatment with FAB122 will be conducted based on the data from the cost questionnaire providing direct and indirect costs associated with the disease, and information from eCRF data existing of hospitalizations, concomitant medication and occurrence of AEs.

The following cost parameters are considered for the cost-utility analysis among study groups:

- Number of contacts classified per specialist and type of contact.
- Number of hospitalizations related to ALS classified per unit of stay and length of stay.
- Specialized equipment / Devices cost per type of Medical Aid.
- Paramedical treatment visits (i.e. physical therapy, rehabilitation, occupational therapist, speech and language therapist, or otherwise specified by the patient).
- Formal care (i.e. health professional) and informal care (i.e. familiar/friend): duration and cost per type of service and overall.
- Employment situation.
- Occurrence of AEs in each group (see section 5.7.1, note: no costs are collected for this).

Descriptive statistics will be displayed for each of the categories above as well as for the costs by category and over all categories for each patient, where costs will be presented in euros. As applicable, duration of a hospitalization (in days) will be presented as average over the patients as well as the total summed duration over all patients per treatment group. Adding of costs and calculation from local tariff to euro will be done via programming, using input from client and DM vendor on used currency and exchange rates to be used by time of Database lock.

It should be noted that most cost-utility analysis fields are free text (in local language), which may make it complicated to derive all the above directly from the data. Also, in the data collected, there is no clear indication whether or not hospitalizations are related to ALS and total costs collected are not consistently entered. Specific data handling strategies may be discussed with the client and the DM vendor, otherwise descriptive statistics will be limited to items as collected, where free text fields will only be listed (without translation).

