## EQ-5D-5L

The EQ-5D descriptive system comprises five dimensions: mobility, self-care, usual activities, pain/discomfort and anxiety/depression. Each dimension has 5 levels (no problems, slight problems, moderate problems, severe problems, extreme problems) and is scored as a 1-digit number (ranging 1-5, respectively) expressing the level for that dimension. The digits for the five dimensions can be combined into a 5-digit number that describes the patient's health state (e.g. 1-1-3-4-5).

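### The SAP gives the EQ-5D-5L score endpoint no score and no change-from-baseline analysis, and the planned cost-utility analysis has no utility input

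*SAP*

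**What the plan says.** Protocol 3.2.2 (QoL) lists as a secondary endpoint "Change from baseline in EuroQoL – 5 Dimensions-5 Levels (EQ-5D-5L) questionnaire score at 24, 48 and 72" weeks, and SAP 4.3 repeats it: "Change from baseline in EuroQoL – 5 Dimensions-5 Levels (EQ-5D-5L) questionnaire score at 24, 48 and 72 weeks".

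SAP 5.6.2 (QoL) then plans the following for EQ-5D-5L: "Frequency and percentage of each level will be presented for each timepoint on each of the dimensions, per treatment". It adds: "The per patient 5-digit number will only be presented in the listing". The derivation in SAP 9.1 stops at the health-state label: "The digits for the five dimensions can be combined into a 5-digit number that describes" the state of the patient.

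For health economics, SAP 4.4 names as an exploratory endpoint "Cost-Utility analysis of treatment with FAB122", and SAP 5.6.4 says that "an exploratory cost-utility analysis for treatment with FAB122 will be conducted". The data sources given there are the cost questionnaire and the eCRF records of hospitalizations, concomitant medication and adverse events. Protocol section 10 gives the same sources. Protocol 11.5 says that health-economic parameters will be handled descriptively and leaves further detail to the SAP.

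**The concern.** A change from baseline needs a single number per patient and visit. Level frequencies per dimension do not give one, and neither does the five-digit label. A statistician who follows the SAP exactly therefore reports distributions of answers and never estimates the endpoint that both documents name.

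The label on the health-economic analysis raises a related problem. A cost-utility analysis sets costs against a utility measure, usually quality-adjusted life years (QALYs). If no utility is derived, the name promises more than the analysis delivers.

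At stake are one secondary endpoint, which the SAP treats as explorative, and one exploratory endpoint. If the score is chosen only after unblinding, the value set and the treatment of deaths become post hoc decisions.

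**Working it through.** The plan states no figure for this point, so there is none to reproduce. The check follows each quality-of-life endpoint from its definition to its output.

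| Step | ALSAQ-40 total | VAS | EQ-5D-5L |
|---|---|---|---|
| Endpoint (SAP 4.3) | change from baseline | change from baseline | change from baseline |
| Single score available | yes, mean of 5 scales (SAP 9.1) | yes, 0 to 100 (protocol 8.1.6) | none; five-digit label only (SAP 9.1) |
| Change from baseline (SAP 5.6.2) | yes | yes | not mentioned |
| Model (SAP 5.6.2) | similar to primary | similar to primary | none |
| Analysis table (SAP 10.3) | 14.2.17.7 | 14.2.17.10 | none; descriptive 14.2.17.8 only |

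Two of the three endpoints reach a treatment comparison. EQ-5D-5L does not.

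**Can the five-digit label serve as the score?** No. Five dimensions at five levels give 5^5 = 3125 possible labels, and their numerical order has no meaning. For example, 21111 (one slight problem) minus 12555 (one slight and three extreme problems) is 8556, so the much better state has the larger number. Neither document defines an index, a value set or a sum score.

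**Does another rule fill the gap?** SAP 5.6 promises descriptive change-from-baseline statistics by visit for every secondary endpoint. That rule has nothing to act on where no scalar score is defined. The VAS is a separate endpoint in both documents, and neither calls it the EQ-5D-5L score or a utility. SAP section 6, which lists changes from the protocol, does not mention EQ-5D-5L or the cost-utility analysis.

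**Cost-utility analysis.** The inputs in protocol section 10 and SAP 5.6.4 are costs, resource use, employment and adverse events. EQ-5D-5L is not among them. The outputs in SAP 5.6.4 are descriptive statistics, with costs by category and overall per patient in euros. The output list has only descriptive tables (14.2.20.1 onward). Neither document mentions a QALY or an incremental ratio.

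**Are the data there?** Yes. Protocol 8.1.6 schedules EQ-5D-5L at baseline and weeks 12, 24, 36, 48, 60 and 72. That is 7 assessments for the roughly 100 patients followed to week 72, and 5 (baseline, 12, 24, 36, 48) for the other two thirds.

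**The case against.** The case for leaving the plan alone has several sound parts. Protocol 11.3.4.3 describes the other secondary endpoints as exploratory, leaves the method for each to the SAP, and allows continuous endpoints to be shown by frequencies as well. SAP 5.6 treats everything outside the testing hierarchy as explorative. Level frequencies by dimension, visit and arm are a legitimate display of ordinal items. The quality-of-life objective still gets treatment estimates from the ALSAQ-40 total and from the VAS, which is collected at the same visits as EQ-5D-5L.

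This limits the weight of the point but does not remove it. The protocol offers frequencies as an addition to the usual summaries of a continuous endpoint, and both documents still name a change in score.

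A reader might infer four stronger things that the documents do not support:

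- *The endpoint is lost.* It is not. The five item levels are collected, so a score can still be derived.
- *The SAP fails to deliver a promised cost per QALY.* Neither document promises one. The protocol's own input list has no utility, and the SAP follows it. The fault is in the name.
- *The health-economic endpoint yields nothing.* Costs by category and overall are summarised.
- *Seven assessments per patient go unused.* Seven applies only to patients followed to week 72; the others have five. The level tables do use the responses.

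**Conclusion.** The point holds for the SAP as written. The secondary endpoint of change in EQ-5D-5L score has no defined score, no change from baseline, no model and no analysis table, so no EQ-5D-5L treatment difference would be estimated at any of its three time points. The exploratory cost-utility analysis is in substance a descriptive cost analysis, and that mismatch begins in the protocol.

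The consequence is moderate. One secondary endpoint outside the testing hierarchy and one exploratory endpoint are affected. The primary test, the key secondary tests and the significance level are not.

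The conclusion assumes that no separate health-economics plan supplies the missing steps. The documents mention separate plans for the PK and DSMB analyses but none for health economics, and protocol 11.5 points to the SAP.

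**What to change.** Before unblinding:

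1. In SAP 9.1, derive an EQ-5D-5L index from the five item levels with one value set, named in advance and used for all countries.
2. In SAP 5.6.2, analyse change from baseline in the index at weeks 24, 48 and 72 with the model used for the VAS and the same handling of deaths and missing data. SAP 5.6.2 applies no intercurrent-event correction or imputation to the other secondary endpoints. Setting the index to 0 after death in this model alone would target a different quantity from the VAS analysis.
3. In SAP 10.3, add a statistical analysis table for EQ-5D-5L next to those for the ALSAQ-40 total and the VAS. Keep the level frequencies.
4. Rename the health-economic analysis a descriptive cost analysis and record this in SAP section 6.

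QALYs may be added descriptively, as the area under the index curve with 0 after death. An incremental cost per QALY should be reported only if the cost data prove usable. SAP 5.6.4 itself warns that most fields are free text in local languages, that total costs are entered inconsistently, and that the link of hospitalizations to ALS is not clearly recorded.

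The EQ-5D-5L change costs one derivation, one further model and one table, with no new data collection. Its small downside is that a single value set will not reflect each country's own preferences. Renaming costs only wording. A cost-per-QALY analysis would not be cheap, because the cost data would have to be made usable first.
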